4.2.2. Infusion Reactions

NIVOLUMAB and/or ipilimumab may induce infusion or hypersensitivity reactions. If such a reaction were to occur, it may manifest with fever, chills, rigors, headache, rash, pruritus, arthralgias, hypo- or hypertension, bronchospasm, or other symptoms.

Infusion reactions should be graded according to Common Terminology Criteria for Adverse Events (CTCAE, Version 4.0) guidelines. Treatment recommendations are provided below and may be modified based on clinical judgment, local treatment standards and guidelines, and/or specific symptoms, as appropriate:

For Grade 1 symptoms: (Mild reaction [eg, localized cutaneous reactions including mild pruritus, flushing, rash.] requires infusion rate to be decreased; intervention may be indicated)

- Decrease the rate of the NIVOLUMAB and/or ipilimumab infusion until recovery from symptoms.
- Remain at bedside and monitor subject until resolution of symptoms. Diphenhydramine 50 mg, may be administered at the discretion of the treating physician.
- When symptoms resolve, restart the infusion at the original infusion rate.
- If a subject has an infusion reaction with NIVOLUMAB and/or ipilimumab, prophylactic preinfusion medications should be given prior to all subsequent NIVOLUMAB and/or ipilimumab infusions.
- The following prophylactic preinfusion medications are recommended prior to future infusions of NIVOLUMAB and/or ipilimumab: diphenhydramine 50 mg (or equivalent) and/or paracetamol 325 to 1000 mg (acetaminophen) at least 30 minutes before additional NIVOLUMAB and/or ipilimumab infusions.

For Grade 2 symptoms: (Moderate reaction [ie, any symptom not listed above (mild symptoms) or below (severe symptoms) such as generalized pruritus, flushing, rash, dyspnea, hypotension with systolic blood pressure > 80 mm Hg], requires infusion interruption but responds promptly to symptomatic treatment [eg, antihistamines, non-steroidal anti-inflammatory drugs, narcotics, corticosteroids, i.v. fluids]; prophylactic preinfusion medications indicated for ≤ 24 hours)

- Discontinue the NIVOLUMAB and/or ipilimumab infusion.
- Begin an i.v. infusion of normal saline, and treat the subject with diphenhydramine 50 mg i.v. (or equivalent) and/or paracetamol 325 to 1000 mg (acetaminophen).
- Remain at bedside and monitor subject until resolution of symptoms. Corticosteroid therapy may be administered at the discretion of the treating physician.
- When symptoms resolve, restart the infusion at 50% of the original infusion rate; if no further complications ensue after 30 minutes, the rate may be increased to 100% of the original infusion rate.

- Monitor subject closely. If symptoms recur, immediately discontinue the infusion; no further NIVOLUMAB and/or ipilimumab will be administered at that visit. Administer diphenhydramine 50 mg i.v., and remain at bedside and monitor the subject until resolution of symptoms.
- If a subject has an infusion reaction with NIVOLUMAB and/or ipilimumab, prophylactic preinfusion medications should be given prior to all subsequent NIVOLUMAB and/or ipilimumab infusions.
- The following prophylactic preinfusion medications are recommended prior to future infusions of NIVOLUMAB and/or ipilimumab: diphenhydramine 50 mg (or equivalent) and/or paracetamol 325 to 1000 mg (acetaminophen) should be administered at least 30 minutes before additional NIVOLUMAB and/or ipilimumab administrations. If necessary, corticosteroids (up to 25 mg of SoluCortef or equivalent) may be used.
- The amount of NIVOLUMAB and/or ipilimumab infused must be recorded.

For Grade 3 or Grade 4 symptoms: (Severe reaction [eg, bronchospasm, generalized urticaria, systolic blood pressure < 80 mm Hg, or angioedema], Grade 3: prolonged [ie, requiring 6 or more hours to respond to symptomatic medication and/or discontinuation of infusion]; recurrence of symptoms following initial improvement; hospitalization indicated for other clinical sequelae [eg, renal impairment, pulmonary infiltrates]. Grade 4: life-threatening; pressor or ventilatory support indicated).

- Immediately discontinue the NIVOLUMAB and/or ipilimumab infusion. No further NIVOLUMAB or ipilimumab will be administered. The amount of NIVOLUMAB and/or ipilimumab infused must be recorded.
- Begin an i.v. infusion of normal saline, and treat the subject as follows: Recommend bronchodilators, epinephrine 0.2 to 1.0 mg of a 1:1,000 solution for subcutaneous administration or 0.1 to 0.25 mg of a 1:10,000 solution injected slowly for i.v. administration, and/or diphenhydramine 50 mg i.v. with methylprednisolone 100 mg i.v. (or equivalent), as needed.
- Remain at bedside and monitor subject until recovery from symptoms.
- Subject should be monitored until the Investigator is comfortable that the symptoms will not recur.
- The Investigator should follow the institutional guidelines for the treatment of anaphylaxis.

In the case of late-occurring hypersensitivity symptoms (eg, appearance of a localized or generalized pruritus within 1 week after treatment), symptomatic treatment may be given (eg, oral antihistamine, or corticosteroids).

4.2.3. Treatment Reactions: Definitions, Monitoring, and Management

Potential toxicities including infusion and post-infusion reactions were defined above for NIVOLUMAB and/or ipilimumab (Section 5.2.2). These events will be closely monitored.

Therapy to prevent or treat local and/or systemic reactions following either study drug administration may include analgesics, antipyretics and antihistamines. Additionally, if necessary, corticosteroids may be temporarily added or increased for up to 7 days after study drug(s) administration.

4.2.4. Dose Limiting Toxicity: Definition, Monitoring, Management

(Version 4.0 of the NCI Common Terminology Criteria for Adverse Events (CTCAE) will be utilized for AE reporting. Version 4.0 of the CTCAE is identified and located on the CTEP website at [HTTP://CTEP.CANCER.GOV/PROTOCOLDEVELOPMENT/ELECTRONIC_APPLICATIONS/CTC.HTM](http://CTEP.CANCER.GOV/PROTOCOLDEVELOPMENT/ELECTRONIC_APPLICATIONS/CTC.HTM). All appropriate treatment areas should have access to a copy of Version 4.0 of CTCAE.)

4.2.4.1. Definition

A DLT is defined as a NIVOLUMAB or NIVOLUMAB with ipilimumab related Grade 3 or greater adverse event other than the exceptions noted occurring within 29 days after the first dose excluding: Grade 3 adverse event of tumor flare (defined as local pain, irritation, or rash localized at sites of known or suspected tumor), Grade 3 rash, Grade 3 immune-related adverse event (irAE, defined below) that resolves to a Grade 1 or less within 28 days, or a transient (resolving within 6 hours of onset) Grade 3 infusion-related adverse event. A Grade 3 irAE that resolves to a Grade 1 or less within 28 days, while not constituting a DLT for dose escalation purposes, may preclude further administration of NIVOLUMAB and/or ipilimumab to the subject.

The following are excluded from the definition of a DLT:

- Grade 3 rash,
- Grade 3 irAE that resolves to a Grade 1 or less within 28 days, or
- A transient (resolving within 6 hours of onset) Grade 3 infusion-related adverse event.

A Grade 3 irAE that resolves to a Grade 1 or less within 28 days, while not constituting a DLT, may preclude further administration of the study drugs to the subject. A DLT will be considered related to 1 or both study drugs unless there is a clear, well-documented, alternative explanation for the toxicity.

Toxicities occurring more than 28 days after the first dose will be monitored and discussed with BMS.

All adverse events that meet DLT criteria, as well as any Grade 3 or 4 infusion reactions whether or not the event is a DLT, must be reported using the rapid notification procedures described in Section 9.6.

Patients who discontinue treatment for toxicities will continue on the protocol radiology evaluation schedule every 12 weeks once the toxicity resolves to obtain relapse-free survival data.

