1.4.3 Rationale for the NIVOLUMAB + ipilimumab clinical study

As of the 15-Feb-2013 clinical cut-off in trial CA209004, in which patients received the combination of ipilimumab with NIVOLUMAB concurrently or sequentially, of the 52 subjects evaluable for response, 21 subjects (40%) had an objective response by modified World Health Organization (mWHO) criteria²⁰⁻²¹. In an additional 2 subjects (4%) there was an unconfirmed objective response. In Cohort 1 (0.1 mg/kg nivolumab + 3 mg/kg ipilimumab), 3 out of 14 evaluable subjects had an objective response by mWHO (21%); 1 CR and 2 PRs with an additional PR by immune-related mWHO criteria (irPR).⁵⁵ In Cohort 2 (1 mg/kg nivolumab + 3 mg/kg ipilimumab), 9 out of 17 evaluable subjects had an objective response by mWHO (53%; 3 CRs (18%), 6 PRs (35%) with two additional subjects experiencing immune-related SD (irSD). In Cohort 2a (3 mg/kg nivolumab + 1 mg/kg ipilimumab), 6 out of 15 response evaluable subjects had an objective response rate by mWHO (40%; 1 CR (7%), 5 PRs (33%) with 2 additional uPRs (13%) and 2 irSDs and 1 irPR). In Cohort 3 (3 mg/kg nivolumab + 3 mg/kg ipilimumab), 3 out of 6 evaluable subjects had an objective response by mWHO (50%; 3 PRs (50%) with 1 additional irPR and 1 irSD. Preliminary analysis revealed 16 of the 52 evaluable subjects (31%) had > 80% reduction in the size of target tumor lesions by the week 12 evaluation. This is compared to < 2% for 3 mg/kg ipilimumab monotherapy based on CA184020 (N=540) and < 3% for nivolumab monotherapy based on CA209003 (N=94, 0.1-10 mg/kg. Follow-up phase II data in the randomized CA209-069 study of nivolumab + ipilimumab versus ipilimumab alone showed a 61% response rate and a 55% rate of grades 3-4 irAEs for the combination at the nivolumab dose of 1 mg/kg and ipilimumab at 3 mg/kg in the induction portion of the trial over the first 12 weeks. These data led to the FDA approval of the combination regimen for unresectable melanoma in 2015²⁰⁻²¹. The most common (reported at > 10% incidence) treatment related AEs with the combination are fatigue, rash, pruritus, diarrhea, lipase increased, pyrexia, ALT increase, AST increased, amylase increased and vitiligo. Although the preliminary data suggests an increase in adverse event frequency of nivolumab combined with ipilimumab compared to ipilimumab monotherapy or nivolumab monotherapy, there were no unexpected adverse events noted in the combination of nivolumab and ipilimumab. In addition, many of the Grade 3-4 adverse events associated with the nivolumab combined with ipilimumab were laboratory in nature, without clinical sequelae and adverse events have been manageable and reversible following intervention dose delays or with systemic steroid treatment. While the grade 3 irAE rate in that trial was 53%, the regimen was felt to be well tolerated, with a high level of clinical activity. The choice of the combination of NIVOLUMAB and ipilimumab at the chosen doses for cohort 4 of the predecessor trial MCC 15651 at Moffitt Cancer Center was based on

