3.4.6 Early Discontinuation Criteria and Procedures

3.4.6.1 Discontinuation of Study Drug

It is the right and duty of the Investigator to discontinue the study drugs of any subject if he feels that discontinuation of the study drugs is necessary to protect the subject, or that there are unmanageable factors that may interfere significantly with the study procedures and/or the interpretation of results.

Administration of the study drugs will be discontinued if the subject develops a DLT, documented relapse, or other intolerability to the study drugs.

Administration of the study drugs may be discontinued during the study for any of the following reasons:

- Adverse event(s)
- Protocol violation
- Subject withdrew consent
- Lost to follow-up
- Other
- Death

For subjects who discontinue the study drugs for any reason, the remaining study visits and associated evaluations (without dosing) should be completed. Patients who discontinue the study drug(s) due to a toxicity will be followed until the toxicity resolves to baseline. Patients will continue to be followed on the protocol schedule for radiology assessments and for relapse free survival. Pharmacokinetic samples will only be collected at the visit following study drug discontinuation.

All subjects will be followed for adverse events for at least 70 days after the last dose of study drugs and for survival follow-up indefinitely until withdrawal of consent or death.

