4.2. Treatment Regimen

4.2.1 Toxicity management

4.2.1.1. Management:

For Grade 1 and 2 adverse events felt due to NIVOLUMAB or NIVOLUMAB with ipilimumab, symptomatic treatment is called for generally without a dose delay. For selected irAEs of grade II, especially colitis and ophthalmologic toxicity, one dose of NIVOLUMAB or NIVOLUMAB with

ipilimumab may be skipped until resolution of the toxicity to Grade 1 or less. Grade 3 irAEs that constitute dose limiting toxicity will cause treatment with NIVOLUMAB or NIVOLUMAB with ipilimumab to be discontinued permanently. For grade III irAEs that do not constitute DLT, do not require more than 2 weeks of systemic steroid treatment, and resolve within 28 days to grade I or less, with either one or no skipped doses, therapy with NIVOLUMAB or NIVOLUMAB with ipilimumab may continue at the same dose(s). There will be no dose reductions of NIVOLUMAB for an individual patient. Management of infusion reactions is defined in section 5.2.2 below.

4.2.1.2. Dose Delay:

NIVOLUMAB with ipilimumab administration should be delayed for the following:

- Any Grade ≥ 2 non-skin, drug-related adverse event, with the following exceptions:
 - Grade 2 drug-related fatigue or laboratory abnormalities do not require a treatment delay
- Any Grade 3 skin, drug-related adverse event
- Any Grade 3 drug-related laboratory abnormality, with the following exceptions for AST, ALT, total bilirubin, amylase and lipase:
 - If a subject has a baseline AST, ALT, or total bilirubin that is within normal limits, delay dosing for drug-related Grade ≥ 2 or greater toxicity
 - If a subject has baseline AST, ALT, or total bilirubin within the Grade 1 toxicity range, delay dosing for drug-related Grade ≥ 3 or greater toxicity
 - Grade 3 amylase or lipase abnormalities that are not associated with symptoms or clinical manifestations of pancreatitis do not require a dose delay. It is recommended to consult with the BMS Medical Monitor for Grade 3 amylase or lipase abnormalities.
- Any adverse event, laboratory abnormality, or intercurrent illness which, in the judgment of the investigator, warrants delaying the dose of study medication.

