4.2.1.3. Discontinuation

Treatment should be permanently discontinued for the following:

- Any Grade 2 drug-related uveitis or eye pain or blurred vision that does not respond to topical therapy and does not improve to Grade 1 severity within the re-treatment period OR requires systemic treatment
- Any Grade 3 non-skin, drug-related adverse event lasting > 7 days, with the following exceptions for drug-related laboratory abnormalities, uveitis, pneumonitis, bronchospasm, diarrhea, colitis, neurologic toxicity, hypersensitivity reactions, and infusion reactions:
- Grade 3 drug-related uveitis, pneumonitis, bronchospasm, diarrhea, colitis, neurologic toxicity, hypersensitivity reaction, or infusion reaction of any duration requires discontinuation

Grade 3 drug-related laboratory abnormalities do not require treatment discontinuation except:

- Grade 3 drug-related thrombocytopenia > 7 days or associated with bleeding requires Discontinuation
- Any drug-related liver function test (LFT) abnormality that meets the following criteria require discontinuation:
 - AST or ALT > 8 x ULN
 - Total bilirubin > 5 x ULN

-
- Concurrent AST or ALT > 3 x ULN and total bilirubin > 2 x ULN
 - Any Grade 4 drug-related adverse event or laboratory abnormality, except for the following events which do not require discontinued.
 - Isolated Grade 4 amylase or lipase abnormalities that are not associated with symptoms or clinical manifestations of pancreatitis. It is recommended to consult with the BMS Medical Monitor for grade 4 amylase or lipase abnormalities.
 - Isolated Grade 4 electrolyte imbalances/abnormalities that are not associated with clinical sequelae and are corrected with supplementation/appropriate management within 72 hours of their onset
 - Dosing interruptions to allow for prolonged steroid tapers to manage drug-related adverse events are allowed. Prior to re-initiating treatment in a subject with a dosing interruption lasting > 6 weeks, the BMS medical monitor must be consulted. Tumor assessments should continue as per protocol even if dosing is interrupted.
 - Dosing interruptions > 6 weeks that occur for non-drug-related reasons may be allowed if approved by the BMS medical monitor. Prior to re-initiating treatment in a subject with a dosing interruption lasting > 6 weeks, the BMS medical monitor must be consulted. Tumor assessments should continue as per protocol even if dosing is interrupted.

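### In the 29-day DLT window, a few kinds of drug-related event are DLTs that end study drug under 4.2.4.1 and 3.4.6.1, but need no discontinuation under 4.2.1.3

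*Combined protocol and SAP*

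**What the plan says.** **What a DLT is.** Section 4.2.4.1 opens: "A DLT is defined as a NIVOLUMAB or NIVOLUMAB with ipilimumab related Grade 3 or greater adverse event other than the exceptions noted". The sentence then sets the time window and names the first exception: "occurring within 29 days after the first dose excluding: Grade 3 adverse event of tumor flare". The other exceptions are Grade 3 rash, a "Grade 3 irAE that resolves to a Grade 1 or less within 28 days", and a Grade 3 infusion-related event that clears within 6 hours. All four are limited to Grade 3, and none names laboratory findings. The synopsis definition matches. The bulleted list in the same section repeats three of the exceptions and omits tumor flare.

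**What a DLT does.** Section 3.4.6.1: "Administration of the study drugs will be discontinued if the subject develops a DLT, documented relapse, or other intolerability to the study drugs". The synopsis and 2.1 also say that a patient with a DLT receives no further study treatment. Section 4.2.5 stops accrual, pending consultation, at 3 of the first 6, 4 of the first 10, or 40% of 20 patients with a DLT.

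**What does not require discontinuation.** Section 4.2.1.3 exempts two kinds of Grade 4 finding:
- "Isolated Grade 4 amylase or lipase abnormalities that are not associated with symptoms or clinical manifestations of pancreatitis"
- "Isolated Grade 4 electrolyte imbalances/abnormalities that are not associated with clinical sequelae and are corrected with supplementation/appropriate management within 72 hours"

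It also exempts Grade 3 laboratory abnormalities, apart from its thrombocytopenia and liver-test criteria. Other Grade 3 non-skin events require discontinuation only if they last more than 7 days, except for a named list (such as colitis and pneumonitis) that does so at any duration.

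**When a laboratory finding is an adverse event.** Sections 5.1.6 and 6.6 give three routes: it leads to discontinuation, it needs therapeutic intervention, or the investigator judges it to be one.

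**The concern.** A drug-related event in the first 29 days can meet the DLT definition, and so end treatment, and also fall under an exemption in 4.2.1.3. No section says which prevails. Two investigators who follow the protocol could then treat the same patient differently, and one of the two outcomes is permanent loss of adjuvant treatment.

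The same classification feeds 4.2.5, the only numeric accrual rule, in a trial whose primary objective is safety and tolerability. These events are foreseeable: section 1.4.3 says of earlier experience with the combination that "many of the Grade 3-4 adverse events associated with the nivolumab combined with ipilimumab were laboratory in nature, without clinical sequelae".

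**Working it through.** **Step 1. Set the rules side by side.** Each event is taken as drug-related and within 29 days of the first dose.

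| Event | 4.2.4.1 with 3.4.6.1 | 4.2.1.3 | Conflict? |
|---|---|---|---|
| Isolated Grade 4 electrolyte abnormality, no sequelae, corrected within 72 hours | An adverse event under 5.1.6 and 6.6 if correction is a therapeutic intervention. Then a DLT: stop | Discontinuation not required | Yes |
| Isolated asymptomatic Grade 4 amylase or lipase | A DLT only if the investigator records an adverse event | Discontinuation not required | Yes, if recorded |
| Grade 3 laboratory adverse event, not an irAE resolving to Grade 1 or less within 28 days, outside the thrombocytopenia and liver-test criteria | DLT: stop | Discontinuation not required | Yes |
| Grade 3 non-immune, non-skin event of 7 days or less, off the any-duration list and not another DLT exception | DLT: stop | Below the 7-day threshold | Yes |
| Grade 3 irAE resolving to Grade 1 or less within 28 days | Not a DLT | Depends on type and duration | Not this conflict |

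For amylase and lipase, the discontinuation route to adverse-event status is circular: the finding is an adverse event if it ends treatment, and it ends treatment as a DLT only if it is an adverse event. That leaves the investigator's recording decision.

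**Step 2. Check the neighboring rules.** Section 4.2.1.2 says "Grade 3 amylase or lipase abnormalities that are not associated with symptoms or clinical manifestations of pancreatitis do not require a dose delay". That is a delay rule, so the conflict over discontinuation rests on 4.2.1.3.

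A related conflict runs the other way. After a Grade 3 irAE that is not a DLT and resolves within 28 days, 4.2.1.1 may allow treatment to continue if its steroid and skipped-dose conditions are met. If that event is non-skin and lasts 8 to 28 days, 4.2.1.3 requires discontinuation.

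**Step 3. Size the effect on 4.2.5.** The plan states no operating characteristic for the rule, so there is no figure to reproduce. Read 40% of 20 as 8 patients, let *p* be the chance that a patient has a counted DLT, and let X*n* be the count in the first *n* patients, taken as independent:

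P(stop) = P(X6 ≥ 3) + P(X6 ≤ 2, X10 ≥ 4) + P(X6 ≤ 2, X10 ≤ 3, X20 ≥ 8)

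For *p* = 0.10, the first term is 1 − (0.5314 + 0.3543 + 0.0984) = 0.0159. The second adds 0.0065 and the third 0.0001.

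| *p* | Stopped by 6 | by 10 | by 20 |
|---|---|---|---|
| 0.10 | 0.0159 | 0.0224 | 0.0225 |
| 0.15 | 0.0473 | 0.0716 | 0.0731 |
| 0.20 | 0.0989 | 0.1544 | 0.1621 |
| 0.25 | 0.1694 | 0.2658 | 0.2884 |
| 0.30 | 0.2557 | 0.3949 | 0.4407 |

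Both inputs are assumptions: the base rate, and the share of patients whose only qualifying event is of a disputed kind (5, 10 or 15 points).
- From a 10% base, the chance of a stop goes from 2% to 7%, 16% or 29%.
- From a 15% base, it goes from 7% to 16%, 29% or 44%.

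The nearest figure in the documents is in 1.4.3: at the same induction doses, 17 of 20 patients continued past 12 weeks, so 3/20 = 15% did not. That is not a DLT rate.

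**The case against.** **The rules may be cumulative.** Section 4.2.1.3 says that discontinuation is not required, which is not an instruction to continue, and 3.4.6.1 adds DLT as a separate ground. A stricter rule for the first 29 days could sit beside a general rule for up to 60 weeks of nivolumab. The reading is coherent, but the protocol states it nowhere, and 4.2.1.3 does not mention DLTs or limit its exemptions to the period after the window. If it is what the sponsor means, one sentence would settle the matter.

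**The scope is narrow.** This stands. A reader might infer that every related Grade 3 or higher event is a DLT, that every short Grade 3 event is caught, or that every lipase rise ends treatment. The documents support none of these. The definition has four exceptions and a 29-day window, which covers the doses on days 1 and 22. A Grade 3 irAE that resolves to Grade 1 or less within 28 days is not a DLT. An asymptomatic lipase rise is not an adverse event by default.

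**The size is assumed.** This also stands. Section 1.4.3 gives no patient-level rate or timing for laboratory events, and its experience covers several dose combinations. The upper increments may include Grade 3 irAEs that 4.2.4.1 excludes and findings never recorded as adverse events, so 29% is probably too high.

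**Safety reporting covers much of this already.** Section 6.3.3 tabulates adverse events by preferred term and grade, with laboratory shift tables, and specifies no DLT analysis. So the conflict bears mainly on individual discontinuation and on 4.2.5, less on the reported safety tables. The tumor flare mismatch is minor, since the first paragraph of 4.2.4.1 and the synopsis both exclude it and patients enter without evidence of disease.

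**Conclusion.** The contradiction is real, limited to the event types marked in the first table and to the 29-day window. It is plainest for a Grade 4 electrolyte abnormality corrected with supplementation. For amylase and lipase it depends on whether the investigator records an adverse event.

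A reader might infer that one such event can halt accrual. It cannot: 4.2.5 needs 3 of 6, 4 of 10 or 8 of 20, and the result is a pause for consultation. These events only add to the count. On an assumed 10% base and 5 to 15 added points, the chance of a stop rises from 2% to between 7% and 29% with no change in the other toxicity. That range shows how sensitive the rule is. It does not estimate what will happen.

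The passages must be reconciled because, as written, they give opposite answers on whether a patient stops treatment. The documents do not show which answer is intended.

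**What to change.** - Reconcile 4.2.4.1, 3.4.6.1, 2.1 and the synopsis with 4.2.1.3, so that no event is both a mandatory stop and exempt from one. If the DLT rule is meant to override the exemptions during the window, or the reverse, say so in each place.
- In the same edit, reconcile 4.2.1.1 with 4.2.1.3 for Grade 3 non-skin irAEs lasting 8 to 28 days.
- Use one DLT exclusion list throughout.
- State in 4.2.5 whether the events exempted in 4.2.1.3 count toward the accrual rule.

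The sponsor decides which rule stands. The cost is protocol wording, and the DLT count may change slightly. No new data are needed.
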